#### **6.2.5.2.3. Analysis Methods**

The probability of a subject achieving freedom from cardioversion (defined above) at 12 months (365 days) will be estimated using Kaplan-Meier survival analysis. The standard error will be approximated using Greenwood's formula. A two-sided 95% log-log confidence interval for the probability at 12 months will be constructed. A two-sided log rank test will be used to assess whether the cardioversion rate differs between treatment groups. If the p-value from the log-rank test is less than the alpha level determined by the Hochberg procedure (described in section 6.5), the objective will be considered met.

Day 0 is defined as the day of the index cryoablation procedure or the day in which drug therapy is initiated. For subjects with at least one cardioversion, the survival date will be set to the date of the first cardioversion. For subjects without any cardioversions through 12 months, those subjects will be censored at the last study contact date recorded on a CRF which may include the last study visit, the exit

date, or the date of death. If a subject without any cardioversions is lost to follow-up, the censoring date will be set to the last known study visit date. For cardioversions occurring on the day of index treatment, survival time will be set to 0.5 days.

The survival curve from 0 to 12 months will be presented for both treatment arms. Counts of all cardioversions administered over 12 months will also be summarized.

**6.2.5.2.4. Determination of Subjects for Analysis**

This analysis will be performed on data from the mITT dataset.

[REDACTED]

[REDACTED]

[REDACTED]

- | [REDACTED]
- | [REDACTED]
- | [REDACTED]
- | [REDACTED]
- | [REDACTED]

[REDACTED]

[REDACTED]

[Redacted text block]

[Redacted text block]

[Redacted text block]

[Redacted text block]

[Redacted text block]

[Redacted text block]

[Redacted text block]

[Redacted text block]

### 6.3. Center Pooling

The STOP AF First study is expected to be conducted at up to 10 sites in Europe and 30 sites in the US, with a total of 210 subjects randomized across all study centers. Per the CIP, each site will enroll between 0 and 31 subjects. The protocol also specifies that no more than 50% of the total enrollment will come from outside of the US.

Data from all sites will be combined without regard to center location for the analysis of the study's primary, secondary [REDACTED] endpoints. However, it will be assessed whether site-to-site and geographical heterogeneity exists in the rate of pre-specified primary endpoints using a fixed-effects meta-analytic approach. This analysis will investigate two things. First, whether sites exhibit significant heterogeneity in event rates, and second, whether geography (a binary variable representing whether a site is located in the US or Europe) moderates any statistically significant heterogeneity that is observed. Models will be fit separately for each primary outcome; in the analysis of each, any center having  $\leq 5$  subjects with complete data will be combined into 'US\_Small' and 'EU\_Small' analysis groups. If a Cochran's Q-test for heterogeneity shows  $p < 0.05$ , it will be taken as evidence of significant heterogeneity between sites. Evidence of between-site heterogeneity will not necessarily preclude pooling data; rather, it will prompt further investigation into the sources of the apparent differences in event rates between sites. At a minimum, findings of analyses on heterogeneity between study sites and between all US and all European sites will be shown in the final report in a table by endpoint.

---

 Cochran, WG. "The Comparison of Percentages in Matched Samples". *Biometrika*, 1950: 37 (3-4), 256-266.

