Medtronic, Inc. is sponsoring the STOP AF First study; a prospective, interventional, multi-center, randomized, controlled, unblinded clinical study. The study will be conducted at up to 30 sites in the US and up to 10 in Europe. Up to 250 subjects will be enrolled. Two hundred and ten (210) subjects will be randomized. The maximum number of subjects that may be randomized at a single center will be 31 subjects (15% of the total subjects randomized). No greater than 50% of the subjects will be enrolled outside of the US. There is no minimum number of required enrollments per site; however, sites will be encouraged to enroll and randomize at least 5 subjects. Subjects will be randomized to either AAD therapy (control arm) or cryoablation (treatment arm). Subjects will be followed at 1 month, 3 months, 6 months, and 12 months following either cryoablation or AAD initiation. Subjects will be exited from the study at the 12 month follow-up visit. At least one Arctic Front Advance CryoAblation Catheter will be used per subject in the treatment arm. Additional catheters may be used in the case of reablation or crossover ablation (at least one per subject).

Figure 1: Study Design

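### For primary efficacy, the planned poolability check compares event rates between sites and regions; no visible text tests or reports whether the cryoablation-versus-AAD effect differs between the US and Europe.

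*SAP*

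**What the plan says.** SAP 6.3 states the pooling rule first: "Data from all sites will be combined without regard to center location". It then promises to assess "whether site-to-site and geographical heterogeneity exists in the rate of pre-specified primary endpoints" by a fixed-effects meta-analytic approach, fitted separately for each primary outcome. Two questions are posed:

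- The first is "whether sites exhibit significant heterogeneity in event rates". If Cochran's Q gives p < 0.05, "it will be taken as evidence of significant heterogeneity between sites".
- The second is whether geography, coded US or Europe, "moderates any statistically significant heterogeneity that is observed".

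Centres with five or fewer subjects with complete data are merged into one US and one European small-centre group. A positive result "will not necessarily preclude pooling data"; it leads to a search for the sources of the rate differences. As a minimum, findings on heterogeneity between sites and between the US and Europe are tabulated by endpoint.

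Three other places matter:

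- SAP 6.2.2.1 makes primary efficacy a comparison of 12-month success between arms.
- Protocol section 6 sets the regional limit: "No greater than 50% of the subjects will be enrolled outside of the US". Protocol 11.4 stratifies the 1:1 randomization by site.
- SAP 6.7 does look for a differential effect of cryoablation against AAD therapy, but its visible subgroups are age, gender, race and ethnicity. Parts of that section are redacted.

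**The concern.** Pooling a two-arm comparison over sites and regions is supported when the treatment effect is reasonably consistent. The event rate is a different quantity. Regions can have the same rate and different effects, or different rates (from case mix or monitoring intensity) and the same effect. A check on rates alone can therefore miss the first situation and raise an alarm in the second.

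At stake is the reading of the result for its purpose. Protocol 4.2 seeks a change to the US indication, and up to half of the subjects may be enrolled elsewhere. A reader will ask whether the effect is seen in US subjects, and the visible plan does not commit to showing it.

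**Working it through.** **The plan's own figure.** SAP 7.1 gives 174 analysed subjects for 69.9% versus 28/61 = 45.9%, two-sided alpha 0.05, power 90%. The mean rate is 0.579.

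n per arm = [1.96·√(2·0.579·0.421) + 1.2816·√(0.699·0.301 + 0.459·0.541)]² / 0.240² = (1.3685 + 0.8680)² / 0.0576 ≈ 86.8, so 87 per arm and 174 in total. Dividing by 0.9 gives 194. Both figures reproduce. The documents give no operating characteristics for the poolability check.

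**Inputs for the check.**
- Success 69.9% (cryoablation) and 45% (AAD): Protocol 15.1.6.
- 210 randomized 1:1 with 10% attrition: 105 × 0.9 = 94.5, taken as 94 per arm.
- Assumptions not in the documents: Europe 25% to 50% of subjects, a binary 12-month outcome, and rates taken across arms.

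**Why a rate can hide an effect.** With 1:1 allocation within site, a region's all-subject rate is about the mean of its two arm rates.

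| Region | Cryo | AAD | Effect (points) | All-subject rate |
|---|---|---|---|---|
| US, planned rates | 69.9% | 45% | +24.9 | 57.45% |
| Europe, no effect | 57.45% | 57.45% | 0 | 57.45% |
| Europe, reversed | 45% | 69.9% | -24.9 | 57.45% |

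The regional rate difference is zero in both European scenarios, so a test of it rejects at about its nominal level.

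**No effect in Europe: power of a treatment-by-region test on the risk difference.** SE² is the sum of p(1-p)/n over the four region-by-arm cells.
- Europe 50% (47 per arm in each region): 0.4579/47 + 0.4889/47 = 0.02014, SE 14.2 points. 24.9/14.2 = 1.75, so power ≈ Φ(1.75 - 1.96) ≈ 42%. The 95% interval for the difference in effects is about ±28 points.
- Europe 25% (70 and 24 per arm): 0.4579/70 + 0.4889/24 = 0.02691, SE 16.4 points. 24.9/16.4 = 1.52, power ≈ 33%.

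Simulation of these cases gives 33-40% for a test on the log odds ratio and 34-43% on the risk difference. The across-arm regional rate test rejects in 4-5%. In simulations with about nine subjects per site and Europe at 20%, 35% or 50%, Cochran's Q on site rates rejects in 3.0-3.6%, and Q followed by a significant regional difference in about 0.5%.

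**Same effect, different rates.** US 75% versus 50%, Europe 55% versus 30%: both effects are 25 points, and the all-subject rates are 62.5% and 42.5%.
- Europe 50%: SE = √(0.525·0.475·2/94) = 7.28 points. 20/7.28 = 2.75, rejection ≈ 78%.
- Europe 25% (140 and 48 subjects, pooled rate 0.574): SE = √(0.574·0.426·(1/140 + 1/48)) = 8.27 points. 20/8.27 = 2.42, rejection ≈ 68%.

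Simulation gives about 68-80%. The treatment-by-region test rejects in about 5-6%, as it should.

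**When the averages do not coincide.** If Europe has no effect because cryoablation success is only 45% there, the regional rate test has some indirect sensitivity: 29-40% with Europe at 20-50%. Requiring a significant site Q first reduces that to 3.5-7%.

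**If rates are taken within arm.** In the no-effect scenario each arm differs by 12.45 points between regions. With Europe at 50% the SEs are 9.9 points (cryo) and 10.3 points (AAD). Testing each at 0.025 (critical value 2.24) gives 16% and 15%, or about 1 - 0.84·0.85 = 29% for either. The check is then not blind, but it would still also respond to a rate shift with a constant effect.

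**Safety.** SAP 7.2 gives 94 × 4% = 3.8 expected events in one arm.

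**The case against.** The best defence is that SAP 6.3 does more than a hostile reading allows, and that little turns on it. Several stronger readings are tempting and should be set aside:

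- A reader might infer that the SAP pools the arms and so misses a regional difference in effect entirely. It says that sites are combined and is silent on arms. Blindness requires rates across arms and regional averages that nearly coincide.
- A reader might infer that geography is looked at only after a significant Q test. Only the moderator step is worded conditionally; the US-Europe table is promised as a minimum. That table nevertheless concerns heterogeneity in rates.
- A reader might construct a more dramatic case: US failure 70% versus 30%, Europe 50% in both arms, 105 per arm without attrition. The rate test then rejects in 4% and the interaction test in 84%. But this needs a 40-point US effect, against the planned 24 to 25, and exact cancellation. It oversells the remedy.
- A reader might extend the point to safety. SAP 6.4.1 measures that endpoint in the cryoablation arm alone, so comparing rates is the right quantity there. Merging small centres also means that the events are not spread over 40 separate units.
- A reader might conclude that no regional effect analysis exists. With redactions in SAP 6.7, one can only say that none is visible.

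It is also true that the check does not gate the primary test, so type I error and the success criterion are unaffected, and the SAP permits further analyses. What remains is that a between-arm claim is supported by a pooling check with no between-arm quantity in it.

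**Conclusion.** The point holds for primary efficacy. The specified check addresses event rates, and nothing visible tests or reports the treatment effect by site or region. If rates are taken across arms, losing the whole planned effect in Europe while the regional averages coincide would be flagged in about 4-5% of trials, no more than by chance. A constant effect with European failure 20 points higher would be flagged in about 68-80%. A treatment-by-region test would detect the lost effect in about 33-40%: better, but not strong.

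These figures assume 94 per arm, a binary outcome, a European share of 25-50% and, for the first pair, coinciding regional averages; the documents fix none of the regional inputs. This is a weakness in interpretation and reporting, worth correcting before analysis. It does not invalidate the primary comparison. Separately, and of minor weight, about four expected safety events make a site-level Q test uninformative.

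**What to change.** In SAP 6.3, for primary efficacy, replace the event-rate Q test with:

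1. the cryoablation-versus-AAD effect in the US and in Europe, each with a 95% confidence interval;
2. a treatment-by-region test, run whatever the site result;
3. a treatment-by-site-group test using the merged small-centre groups already defined.

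If event rates are also tabulated, say whether they are across or within arms. For safety, give event counts by site group and an exact US-Europe comparison in the cryoablation arm.

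The cost is one section of SAP wording: no new data, and no change to the primary test or sample size. The drawback is low interaction power, below 50% even if the whole planned effect is absent in Europe. The SAP should therefore say that a non-significant interaction is not evidence of consistency and that the regional intervals carry the interpretation.

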Essentially, this process goes through the hypothetical exercise of sequentially assuming unobserved control arm subjects are successes, and unobserved treatment arm subjects are failures the day after being lost to follow-up until the log-rank test supports a different conclusion (in this case, when  $p \geq 0.05$ ). This first subject for which  $p < 0.05$  is no longer true is the point at which the analysis 'tips'. Larger numbers of treatment failures and control successes needed to change the conclusion indicate findings that are more robust to informative censoring. If the primary efficacy analysis as specified in section 6.2.2.4 shows  $p \geq 0.05$ , the tipping point analysis will be modified to quantify how many treatment arm successes and control arm failures would be necessary to reach a different conclusion for the hypothesis test.

The primary safety endpoint is only measured in the cryoablation arm. As such, the algorithm to find the tipping point of the primary safety algorithm is slightly different. Like with the efficacy tipping point analysis, data will be sorted by ascending event times, and subjects who are censored prior to 365 days are assigned an event time equal to (date of last contact - index ablation date). Then, for each observation:

- 1) If a failure is observed, skip steps 2 and 3;
- 2) If the observation is censored, set time = time + 1 and event = 1.
- 3) Apply the log-rank test specified in section 6.2.3.4 to find the new two-sided p-value and 95% log-log confidence interval.
- 4) If  $P$  is still  $< 0.05$  and a larger event time  $< 365$  exists, repeat the process with that observation; otherwise stop.

The first observation where the confidence interval includes 12.0% is the tipping point for the primary safety analysis. This analysis will be performed in the CTR dataset. For either primary endpoint, if fewer than 5 subjects have missing data, a worst-case analysis will be done instead of a tipping point analysis.

## 6.5. Adjustments for Multiple Comparisons

A Hochberg multiple testing procedure will be utilized to maintain an overall type I error rate of 0.05 for the four hypotheses being tested among the two secondary objectives. Testing for these objectives will be performed if the primary objectives are met.

The Hochberg procedure is a stepwise procedure and will be implemented as follows. The four hypotheses are abbreviated as H(1), H(2), H(3), and H(4). For each of these, p-values will be calculated and sorted  $p(1) < p(2) < p(3) < p(4)$ . The decision rule to accept or reject each hypothesis will follow the step-up algorithm, where  $\alpha=0.05$ :

- Step 1: If  $p(4) \geq \alpha$ , accept H(4) and go to Step 2, otherwise reject all hypotheses and stop
- Step 2: If  $p(3) \geq \alpha/2$ , accept H(3) and go to Step 3, otherwise reject H(3), H(2) and H(1) and stop
- Step 3: if  $p(2) \geq \alpha/3$ , accept H(2) and go to Step 4, otherwise reject H(2) and H(1) and stop
- Step 4: If  $p(1) < \alpha/4$ , reject H(1); otherwise accept H(1)

In practice, this adjustment may be done simultaneously on a dataset from the four p-values produced,

[REDACTED]

[REDACTED]

[REDACTED]

## 6.6. Interim Analyses

No interim analyses are planned.

## 6.7. Subgroup Analyses

A limited number of additional analyses will be performed to evaluate evidence for a differential effect of cryoablation vs. AAD therapy on the primary and secondary endpoints within subgroups of subjects.

At the time of this SAP, current FDA guidance recommends additional evaluation of primary objectives within the following demographic subgroups:

- Age (calculated as [year of randomization date – year of birth])
- Gender (captured as male or female by the CRF, with a third level for no response)
- Race (White, Black or African American, Asian, American Indian or Alaskan Native, Native Hawaiian or Other Pacific Islander, Other, Not Stated)
- Ethnicity (Hispanic or Latino, or not)

Subgroup analyses will be performed separately for each of the demographic variables listed above, using Kaplan-Meier survival methods. Handling of censoring, visit windows, etc. will be consistent with what is described in the corresponding general methods above in section 6.2 for each objective. [REDACTED]

[REDACTED]

[REDACTED]

[REDACTED]

[REDACTED]

Demographic strata with <5 events will be combined with other strata if the resulting combination is still deemed analytically meaningful, or may be ignored due to the sparseness of information. Age will be calculated as [year of randomization date – year of birth] as the case report form does not collect the exact date of birth for a subject. For subgroup analysis, age will be divided into quartiles. If the overall log-rank test of equality over strata is significant for strata with more than two levels, Tukey's range test will be used to adjust type I error for the comparison between multiple subgroups. Subgroup analyses will be performed in the same datasets in which the corresponding primary objectives are analyzed.

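### SAP 6.7 seeks a differential effect of cryoablation versus AAD, but the only test in its unredacted text compares demographic levels with each other; for the two-arm endpoints a treatment-by-subgroup test should be confirmed or added

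*SAP*

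**What the plan says.** SAP 6.7 gives the purpose of the subgroup analyses as to "evaluate evidence for a differential effect of cryoablation vs. AAD therapy on the primary and secondary endpoints within subgroups of subjects". The variables are age, gender, race and ethnicity. On method, the visible text says: "Subgroup analyses will be performed separately for each of the demographic variables listed above, using Kaplan-Meier survival methods". Several redacted blocks follow.

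The text then resumes with a rule for sparse levels ("Demographic strata with <5 events will be combined with other strata", where that is meaningful) and a rule for age: "For subgroup analysis, age will be divided into quartiles". Next comes the only test that can be read: "If the overall log-rank test of equality over strata is significant for strata with more than two levels", then "Tukey's range test will be used to adjust type I error for the comparison between multiple subgroups".

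On data, "Subgroup analyses will be performed in the same datasets in which the corresponding primary objectives are analyzed". By SAP 6.2.2.5 and 6.2.3.5 these are the mITT cohort (both arms) for efficacy and the CTR cohort (cryoablation arm only) for safety. SAP 6.4.1 confirms that "The primary safety endpoint is only measured in the cryoablation arm". SAP 6.2.4 plans no AAD comparison for quality of life.

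**The concern.** A differential effect is a treatment-by-subgroup question: does the contrast between cryoablation and AAD change from one level to another? A log-rank test of equality across levels asks whether, for example, older subjects fail sooner than younger ones. On a two-arm endpoint, treatment does not enter that comparison at all. A demographic factor that only predicts recurrence will trigger the rule and the pairwise follow-up, although the benefit of ablation is the same in every level. A real difference in benefit can pass unnoticed if the pooled outcome happens to be similar across levels.

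SAP 6.7 ties these analyses to FDA guidance on demographic subgroups, and the trial supports a US indication expansion. Readers will therefore take the results as evidence on consistency of effect, which this test does not provide.

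The stated aim also covers endpoints for which a cryo-versus-AAD effect cannot be estimated as planned. Primary safety is single-arm. Quality of life is a within-arm change tested by paired t-test (SAP 6.2.4.1.3 and 6.2.4.2.3), to which the Kaplan-Meier methods named in 6.7 do not apply.

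**Working it through.** **What the test compares.** The trial has two arms, and the section uses the word strata for demographic levels. Strata with more than two levels are therefore variables such as age quartile or race, and the visible test compares outcomes between those levels.

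**Inputs from the plan.** Success 69.9% (cryo) and 45.9% (AAD), 1:1 allocation and 10% attrition (SAP 7.1); 210 randomized (SAP 4); age in quartiles (SAP 6.7).

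**Anchor.** Section 6.7 has no figure of its own, so the efficacy sample size was reproduced first:

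n per arm = [1.960·√(2·0.579·0.421) + 1.282·√(0.699·0.301 + 0.459·0.541)]² / 0.240² = (1.368 + 0.868)² / 0.0576 ≈ 86.8, so 87 per arm and 174 in total. The computed power is 0.9005 (the SAP states 0.901). With attrition, 174/0.90 = 193.3, so 194. The plan's figures reproduce.

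**Overall hazard ratio implied.** ln(0.699)/ln(0.459) = 0.358/0.779 = 0.46.

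**Simulation.** N = 210, four equal quartiles, exponential failure times, 10% dropout. Each simulated trial was tested at 0.05 by (i) the four-group log-rank test across quartiles with arms pooled, and (ii) a 3-df heterogeneity chi-square of the within-quartile log-rank O−E statistics. The hazard gradients and subgroup hazard ratios are assumptions; the documents give none.

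| Scenario | Across-level log-rank rejects | Heterogeneity test rejects |
|---|---|---|
| No prognostic effect, no effect difference | about 5% | about 5% |
| Prognostic only, hazard ×1.25 per quartile (1.25³ = 1.95-fold range), HR 0.46 throughout | 42% | about 5% |
| Prognostic only, hazard ×1.5 per quartile (1.5³ = 3.4-fold range), HR 0.46 throughout | 95% | about 5% |
| HRs 0.2, 0.3, 0.8, 1.3; pooled 12-month outcomes equal | about 5% | 74% |
| Same HRs; AAD success 45.9% in every quartile | 70% | 79% |

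Repeat runs differ by a few percentage points, which does not change the reading. The fourth row needs AAD success of about 35%, 40%, 54% and 62% across quartiles, rising as the benefit falls.

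**Check under a different model.** Constant hazard from day 90 to day 365, with a Cox likelihood-ratio interaction test and 1,000 trials per scenario:

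- Purely prognostic two-level factor: 42.9% (across-level) against 6.2% (interaction) at a between-level hazard ratio of 1.5, and 86.9% against 6.1% at 2.0.
- Purely prognostic quartiles with a two-fold hazard range: 47.9% against 4.1%.
- Real effect difference with equal pooled outcomes: treatment differences of 48 and 0 points gave 3.8% against 95.6%; 40 and 8 points gave 4.6% against 65.7%.

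Both models show the same pattern.

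**The case against.** The strongest objection is the redaction. The blacked-out blocks stand exactly where a model or treatment contrast would be described. The quoted sentence mentions the overall log-rank test as if it had already been introduced, and it states no method for a two-level variable such as ethnicity. It may be only a follow-up rule, and the hidden text could specify an interaction test or confine the level comparison to safety. This stands. A reader might infer that the SAP has no interaction test, or that the rule is wrong whatever the hidden text says; neither can be supported from what is visible.

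Second, for single-arm safety a comparison between levels is the only one possible and is legitimate. This also stands, so the criticism is confined to the two-arm endpoints.

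Third, a reader might infer that a reversal of effect in one subgroup would give no signal. That goes too far. Kaplan-Meier evaluation of the efficacy objective within subgroups would naturally show both arms' curves, where a reversal could be seen. The 5% figure also needs prognosis to cancel the effect difference; with one common AAD hazard the across-level test rejects in about 70% of trials. What remains is that such a rejection looks the same as one caused by prognosis.

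Fourth, the 95% figure rests on a 3.4-fold hazard range that no document supports. The milder two-fold range still gives 42%.

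Finally, no success criterion or sample size depends on these analyses, and SAP 3 allows further analyses. That limits the consequence but does not make the visible test fit its stated aim.

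**Conclusion.** The concern holds in limited form. In the unredacted text of SAP 6.7, the stated aim and the only stated test do not match for primary efficacy, healthcare utilization and cardioversion. Under the assumed gradients, the test would present a purely prognostic factor as a subgroup finding in roughly four to nine trials in ten, where a proper heterogeneity test stays near its nominal 5%. Its ability to pick up a real effect difference ranges from about 5% to about 70%, depending on how prognosis runs across the levels. In no case does a significant result identify an interaction.

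These sizes rest on assumed subgroup effects, equal level sizes and constant hazards. The absence of a treatment contrast in the visible test does not. For primary safety and quality of life, the flaw is one of labelling: no cryo-versus-AAD differential effect is estimable as planned. The matter is worth correcting because the repair is simple. It does not threaten the primary conclusions or the Hochberg family.

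**What to change.** For primary efficacy, healthcare utilization and cardioversion, check the unredacted SAP 6.7 for a treatment-by-subgroup test. If there is none, add one: a Cox model interaction, or heterogeneity of the within-subgroup log-rank statistics. State that the differential-effect assessment, and any adjustment for multiple comparisons, rests on that test and not on the equality-across-levels test. Report the cryo-versus-AAD effect (difference in 12-month Kaplan-Meier success, or hazard ratio) with a 95% CI in each subgroup.

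State also that power for interaction is low. Age quartiles leave about 210/8 ≈ 26 subjects per arm per level, so a non-significant interaction is not evidence of a consistent effect.

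For primary safety and quality of life, keep the summaries by level but label them descriptive results in the cryoablation arm. For quality of life, name a method suited to change scores.

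The cost is a short SAP revision and a little programming. No extra data or subjects are needed, and the primary analyses do not change.
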